### **Transfusion-free interval before Week 13 and Week 26**

For platelet transfusion, only subjects with response assessments at specific visits (Week 13 or 26) are included in the transfusion-free interval. The same rule applies to RBC transfusion.

### **Maximum duration of Platelet and RBC transfusion free**

This analysis will be only performed for the subgroup of subjects with baseline transfusion dependent.

### **Proportion of subjects who becomes transfusion independent**

This analysis will be only performed for the subgroup of subjects with baseline transfusion dependent.

### **Transfusion frequency and amount**

The transfusion frequency and amount and the proportion of subjects with transfusion decrease will be only performed for the subgroup of subjects with baseline transfusion dependent.

### **Overall survival**

Analysis of overall survival will be based on the FAS. If a subject is not known to have died, survival will be censored at the date of last contact.

## **2.8 Safety analyses**

For all safety analyses, the safety set will be used. All listings and tables will be presented for all subjects.

Safety summaries (tables, figures) include only data from the on-treatment period with the exception of baseline data which will also be summarized where appropriate (e.g., change from

baseline summaries). In addition, a separate summary for death including on treatment and post treatment deaths will be provided. In particular, summary tables for AEs will summarize only on-treatment events, with a start date during the on-treatment period (treatment-emergent AEs).

The on-treatment period lasts from the date of first administration of study treatment to 30 days after the date of the last actual administration of eltrombopag.

### **2.8.1 Adverse events (AEs)**

#### **Coding and grading**

Adverse events will be coded using the Medical dictionary for regulatory activities (MedDRA) Terminology and their severity assessed according to the Common Terminology Criteria for Adverse Events (CTCAE) version 4.03.

#### **General rules for AE Reporting**

AE summaries will include all AEs occurring during on treatment period. All AEs collected in the AE (e)CRF page will be listed along with the information collected on those AEs e.g. AE relationship to study drug, AE outcome etc. AEs with start date outside of on-treatment period will be flagged in the listings.

AEs will be summarized by number and percentage of subjects having at least one AE, having at least one AE in each primary system organ class (SOC) and for each preferred term (PT) using MedDRA coding. A subject with multiple occurrences of an AE will be counted only once in the respective AE category. A subject with multiple CTCAE grades for the same preferred term will be summarized under the maximum CTCAE grade recorded for the event. AE with missing CTCAE grade will be included in the 'All grades' column of the summary tables.

In AE summaries, the primary system organ class will be presented alphabetically and the preferred terms will be sorted within primary SOC in descending frequency. The sort order for the preferred term will be based on their frequency.

The following adverse event summaries will be produced for AEs occurring during the on-treatment period; overview of adverse events and deaths, AEs by SOC and PT, summarized by maximum CTCAE grade, summarized by relationship (all AEs and AEs related to eltrombopag/CsA/r-ATG), seriousness (SAEs and non-SAEs), leading to treatment discontinuation, leading to dose interruption/changes, requiring additional therapy and leading to fatal outcome. Specifically, CTC grade  $\geq 3$  adverse events will be summarized for AEs by SOC and PT.

Furthermore, AE occurring during the on-treatment period will be summarized by subgroup summarized by the above subgroups listed in [section 2.2.1](#). These summaries include: AEs by SOC and PT, AEs with suspected relationship to eltrombopag by SOC and PT and SAEs by SOC and PT.

In addition, on treatment adverse events will be summarized by SOC and PT and by periods (by  $\leq 30$  days,  $>30$  to  $\leq 90$  days,  $>90$  to  $\leq 180$  days,  $>180$  to  $\leq 360$  days). Time of onset of first episode will be used when experiencing the same episode in a subject.

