Participants should be seen for all visits/assessments as outlined in the assessment schedule ([Table 8-1](#)) or as close to the designated day/time as possible. Missed or rescheduled visits should not lead to automatic discontinuation. Participants who prematurely discontinue eltrombopag for any reason should be scheduled for an end of treatment (EOT) visit as soon as possible, at which time all of the assessments listed for the EOT visit will be performed. At this EOT visit, all dispensed investigational product should be reconciled, and the AE and concomitant medications recorded on the CRF. After that, the safety follow-up visit will be performed 30 days after the last administration of eltrombopag, and then participants should be seen for survival follow-up and in visits for efficacy and/or clonal evolution assessments.

Participants who discontinue from study treatments will have efficacy assessments at defined time points (Week 13, Week 26, Week 52 and yearly after), unless or until the occurrence of no response at Week 26, relapse or alternative SAA treatment (whichever comes first). Survival and clonal evolution data will be collected for all participants up to Year 3 (Week 156).

Allowed visit windows are specified as follows:

- Following dose modification, each visit must be completed \pm 3 days until dose stabilization,
- After stabilization of dose, each visit must be completed \pm 7 days,
- The efficacy assessment visits in core treatment part (Week 13 and Week 26) must be completed \pm 3 days, and Week 52 visit in extension part must be completed \pm 7 days. Week 104 and Week 156 visits in follow-up part must be completed \pm 30 days
- The safety follow-up visit after EOT must be completed \pm 7 days.

Because the dose of eltrombopag and CsA may be adjusted based on platelet count and due to safety reasons assessed at any visit, after any dose adjustment or interruption of eltrombopag or CsA the participant should visit hospital weekly at least for 2 weeks, and after stabilization of dose, the participant should visit every 2 weeks in the core treatment part. In the extension part, participants should visit hospital at least every 2 weeks until stabilization of dose; every 4 weeks after stabilization of dose. Stabilization of eltrombopag/CsA dose is defined as no dosing change for at least 4 weeks. If the dose is changed at visiting every 4 weeks, the participant should visit hospital from the next visit until stabilization of dose.

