As per [Section 4.6](#), during a Public Health emergency as declared by Local or Regional authorities i.e. pandemic, epidemic or natural disaster that limits or prevents on-site study visits, alternative methods of providing continuing care may be implemented by the investigator as the situation dictates. If allowable by a local Health Authority and depending on operational capabilities, phone calls, virtual contacts (e.g. tele consult) or visits by site staff to the

participant's home, can replace on-site study visits, for the duration of the disruption until it is safe for the participant to visit the site again.

Table 8-1 Assessment Schedule

Period	Screening	Core treatment part												Extension part		EOT		Long-term Follow-up	
Visit Name	Screening	Day 1	Week 1	Week 2	Week 3 / 5 / 7	Week 4 / 8	Week 6	Week 9/11/15/17/19/21/23/25 when dose adjusted		Week 10/12/14/16/18/20/22/24		Week 13	Week 26	Week 28 to Week 50 ¹	Week 52	End of treatment	Safety follow-up	Survival follow-up	Year 2 / Year 3
Days	-30 to -1	1	8	15	22 / 36 / 50	29 / 57	43	64 to 176		71 to 169		92	183	197 to 351	365	EOT	30 days after EOT	every 3 months	729 / 1093
Informed consent	X																		
Demography	X																		
Medical history/current medical conditions	X																		
Characteristics of SAA	X	X																	
Inclusion / Exclusion criteria	X	X																	
Supportive therapy	X	X	X	X	X	X	X	X		X	X	X	X	X	X			X ²	
Concomitant medications	X	X	X	X	X	X	X	X		X	X	X	X	X	X	X			
Incidence of transfusion	X	X	X	X	X	X	X	X		X	X	X	X	X				X ²	
Physical Examination	Full body examination	S	S	S	S	S	S	S		S	S	Full body examination	S	Full body examination	Full body examination	S			
Vital Signs	X	X	X	X	X	X	X	X		X	X	Once a month	X	X	X				

Period	Screening	Core treatment part											Extension part		EOT		Long-term Follow-up	
Visit Name	Screening	Day 1	Week 1	Week 2	Week 3 / 5 / 7	Week 4 / 8	Week 6	Week 9/11/15/17/19/21/23/25 when dose adjusted	Week 10/12/14/16/18/20/22/24	Week 13	Week 26	Week 28 to Week 50 ¹	Week 52	End of treatment	Safety follow-up	Survival follow-up	Year 2 / Year 3	
Days	-30 to -1	1	8	15	22 / 36 / 50	29 / 57	43	64 to 176	71 to 169	92	183	197 to 351	365	EOT	30 days after EOT	every 3 months	729 / 1093	
ECOG or Lansky performance status	X																	
Height	X													Pediatric participants	Pediatric participants	Pediatric participants		
Body Weight	X									X	X		X	X				
Standard 12 lead ECG	X ³	X ³								X	X		X	X				

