**Figure 1-1 Study design**

Eligible subjects will be enrolled into the study and will receive eltrombopag (from Day 1 to Week 26) concomitantly with r-ATG (on Days 1-5) and CsA (from Day 1 to Week 26) in the core treatment part.

Efficacy assessments will be performed at Week 13 and Week 26 in the core treatment part of the study.

Participants who are assessed as responders (meeting CR or PR criteria) at Week 26 are eligible to the extension part of the study and continue treatment with eltrombopag and CsA after Week 26.

Study treatment should be discontinued if the participant is not assessed as a responder at Week 26.

During the extension part, eltrombopag treatment will be provided up to Week 52. CsA will be maintained or tapered at the investigator's discretion according to local practice, with a total duration of at least 2 years (18 months after Week 26).

End of treatment assessments will be performed after eltrombopag discontinuation anytime during the study. After that, safety follow-up visit will be performed 30 days after the discontinuation of eltrombopag, and participants will enter the long-term follow-up part, with yearly efficacy and clonal evolution assessments up to Year 3 (Week 156).

For non-responders at Week 26, and participants who relapse or receive alternative SAA treatment, safety follow-up visit will be performed 30 days after the discontinuation of eltrombopag, and then clonal evolution and survival will continue to be followed up to Year 3 (Week 156).

Participants who prematurely discontinue eltrombopag will have efficacy assessments at defined time points (Week 13, Week 26, Week 52 and yearly after), unless or until the occurrence of no response at Week 26, relapse or alternative SAA treatment (whichever comes first). Survival and clonal evolution data will be collected for all participants up to Year 3 (Week 156).

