## **General analysis conventions**

**Pooling of centers:** Unless specified otherwise, data from all study centers will be pooled for the analysis. Due to expected small number of patients enrolled at centers, no center effect will be assessed.

**Qualitative data** (e.g., gender, race, etc.) will be summarized by means of contingency tables; a missing category will be included as applicable. Percentages will be calculated using the number of patients in the relevant population or subgroup as the denominator.

**Quantitative data** (e.g., age, body weight, etc.) will be summarized by appropriate descriptive statistics (i.e. mean, standard deviation, median, minimum, and maximum and first and third quartiles when appropriate). PK parameters except Tmax will be summarized by appropriate descriptive statistics (n, arithmetic mean, CV% mean, standard deviation (SD), median, geometric mean, CV% geo-mean, minimum and maximum).

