### **On-treatment assessment/event and observation periods**

For adverse event reporting the overall observation period will be divided into three mutually exclusive segments:

1. ***pre-treatment period***: from day of patient's informed consent to the day before first administration of study treatment
2. ***on-treatment period***: from date of first administration of study treatment to 30 days after date of last administration of eltrombopag.
3. ***post-treatment period***: starting at day 30+1 after last dose of eltrombopag.

Safety summaries (tables, figures) include only data from the on-treatment period with the exception of baseline data which will also be summarized where appropriate (e.g. change from baseline summaries). In addition, a separate summary for death including on treatment and post treatment deaths will be provided. In particular, summary tables for adverse events (AEs) will summarize only on-treatment events, with a start date during the on-treatment period (**treatment-emergent** AEs).

However, all safety data (including those from the post-treatment period) will be listed and those collected during the pre-treatment and post-treatment period will be flagged.

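### The AE-by-period table stops at Day 360, while the on-treatment period of a participant dosed to Week 52 runs to about Day 395

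*SAP*

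**What the plan says.** SAP 2.8.1, under the general rules for AE reporting, states that AE summaries include all AEs of the on-treatment period. Later in the same section it adds that "on treatment adverse events will be summarized by SOC and PT and by periods". It lists four periods: up to 30 days, more than 30 to 90, more than 90 to 180, and more than 180 to 360. There is no later period. For repeated events, "Time of onset of first episode will be used when experiencing the same episode in a subject".

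SAP 2.1.1 defines the on-treatment period as "from date of first administration of study treatment to 30 days after date of last administration of eltrombopag", and SAP 2.8 repeats this. On dosing, SAP 1.1 says: "During the extension part, eltrombopag treatment will be provided up to Week 52". Protocol Table 8-1 puts the Week 52 visit on Day 365. Protocol Section 8, in its list of visit windows, says the "Week 52 visit in extension part must be completed" within 7 days either side.

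The final-analysis SAP of 11-Nov-2024 repeats the four periods and the on-treatment definition in its own sections 2.8.1 and 2.1.1.

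**The concern.** A table described as covering on-treatment AEs should have a place for each of them. This one has no place for an AE that first starts after Day 360, although the SAP's own definition of on-treatment runs past that day for anyone who completes Week 52.

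The uncovered stretch has a particular use: it contains the weeks just after eltrombopag stops. The protocol requires AE follow-up for 30 days after the last dose (Sections 6.5.2 and 10.1.1), so the data will exist. No other summary of AE onset over time is specified in SAP 2.8.1. A reader of this table would see nothing for that month and could take the absence as a finding. A participant whose only event of a given preferred term began after Day 360 would also be counted in the overall table and in none of the four periods, so the two tables would disagree without explanation.

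**Working it through.** **Inputs**
- Week 52 visit: Day 365 (Protocol Table 8-1).
- Week 52 visit window: 7 days either side (Protocol Section 8).
- Last planned eltrombopag: Week 52 (SAP 1.1; Protocol 6.1.5).
- End of on-treatment period: last eltrombopag dose plus 30 days (SAP 2.1.1 and 2.8).
- Upper limit of the last period: 360 days (SAP 2.8.1).

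**Reproducing the plan's day numbers.** Study day = 7 × week + 1. Weeks 13, 26, 52, 104 and 156 give Days 92, 183, 365, 729 and 1093, all as in Table 8-1.

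**Uncovered days.** End = last dose day + 30. Uncovered = end − 360.

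| Last eltrombopag dose | On-treatment end | Uncovered days | Share of on-treatment period |
|---|---|---|---|
| Day 330 | 360 | 0 | 0% |
| Day 358 (window, −7) | 388 | 28 | 28/388 = 7.2% |
| Day 365 (planned) | 395 | 35 | 35/395 = 8.9% |
| Day 372 (window, +7) | 402 | 42 | 42/402 = 10.4% |

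With a last dose on Day 365, the 35 uncovered days are the last 5 dosing days (361 to 365) and all 30 days after dosing (366 to 395). With a last dose on Day 358, 28 of the 30 post-dose days are uncovered.

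**Which events are affected.** Because of the first-episode rule, an event that began by Day 360 and recurred later stays in its earlier period. Only events with first onset after Day 360 have no period.

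**Day convention.** The SAP does not say whether the periods count study days or days elapsed since Day 1. The table above uses study days. With elapsed days, the last period would reach study Day 361 and each non-zero gap would be one day shorter.

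**Which analysis is affected.** In the final analysis, every Week 52 completer has passed Day 395. The primary analysis can be touched too. Three participants were enrolled by 08-Dec-2020 and the last first visit was on 03-Dec-2021 (Protocol amendment summaries). Week 26 for the last participant therefore falls in June 2022 or later, by which time those early participants could have passed Day 402.

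**The case against.** The strongest reply is that nothing is lost. An on-treatment AE starting after Day 360 still appears in the tables by SOC and PT, by grade, by relationship and by seriousness, and in the AESI tables. All AEs are listed, and listings show the study day, so the onset can be recovered. This stands. It confines the defect to one descriptive table, and a reader who inferred that late AEs drop out of the safety analysis would be wrong.

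A second reply is that the gap is smaller than its ceiling. Eltrombopag is provided up to Week 52, and the 7-day window applies to the visit. Extension supply is for participants considered to need it, and Protocol Table 6-4 provides for dose reduction and interruption after Week 26. Anyone whose last dose is by Day 330 has no uncovered day. This also stands: 35 of 395 days is the planned case, 42 of 402 needs dosing through the whole window, and neither applies to early stoppers.

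A stronger reading is tempting: that percentages based on the whole safety set understate late AEs, because Week 26 non-responders have left. The documents do not support it, for three reasons.
- Non-responders stop at about Day 183 and remain on-treatment to about Day 213 (183 + 30). They are still on-treatment when the last period opens on Day 181 and contribute 33 of its 180 days. A denominator of those on-treatment at its start would still count them.
- The periods last 30, 60, 90 and 180 days. Assume a Week 26 response of 50% to 70% (the range of rates cited in Protocol 1.1), no earlier dropout, and all responders dosed through Day 360. The last period then averages 0.5 × 180 + 0.5 × 33 = 106.5 to 0.7 × 180 + 0.3 × 33 = 135.9 days per participant, against at most 30 in the first. Unequal width pushes late percentages up, while departures and the first-episode rule push them down. The net direction is not established.
- The by-period sentence names no denominator. If the general rule in SAP 2.1 applies, the result is a crude incidence in the safety set, which is a valid descriptive choice.

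**Conclusion.** The point holds for the missing period. As written, the by-period table cannot deliver what SAP 2.8.1 promises, because on-treatment AEs with first onset on Days 361 to 395 have nowhere to go. The gap is 35 of 395 days (8.9%) for a participant whose last dose is on Day 365, and at most 42 of 402 days (10.4%). For Week 52 completers it takes in all or nearly all of the month after eltrombopag.

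This rests on the SAP's own on-treatment definition, on dosing up to Week 52, and on reading the periods as study days. It needs no assumption about response rates or the number who leave treatment. The number of AEs affected cannot be known from the documents.

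The severity is minor: one descriptive safety table is incomplete and will not reconcile with the overall table. No event disappears from the report, and no claim that late AE rates are understated follows.

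**What to change.** In section 2.8.1 of both the primary-analysis and the final-analysis SAP, either redefine the last period as more than 180 days to the end of the on-treatment period, or keep the four periods and add a fifth for onset after Day 360. The fifth period is slightly more informative, because it largely isolates the weeks after eltrombopag stops. State in the same sentence that the periods count study days.

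Showing the number of participants still on-treatment in each period would help the reader, but it is optional.

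The cost is one sentence in each SAP and, for the second option, one more category in the table. Data collection, treatment and the primary endpoint are untouched.

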### **2.8.1.1 Adverse events of special interest / grouping of AEs**

An adverse event of special interest is a grouping of adverse events that are of scientific and medical concern specific to compound eltrombopag. These groupings are defined using MedDRA terms, SMQs (standardized MedDRA queries), HGLTs (high level group terms), HLT (high level terms) and PTs (preferred terms). Customized SMQs (Novartis MedDRA queries, NMQ) may also be used. A NMQ is a customized group of search terms which defines a medical concept for which there is no official SMQ available or the available SMQ does not completely fit the need. It may include a combination of single terms and/or an existing SMQ, narrow or broad.

At the project level, a sas dataset named eCRS contains the exact composition of the adverse events groupings will be used to map reported adverse events to the notable adverse events groupings. This dataset may be updated (i.e., it is a living document) based on review of accumulating trial data, and it is the most up to date version at the time of DB lock that will be used. Note that certain adverse events may be reported within multiple groupings.

For each specified AESI, number and percentage of patients with at least one event of the AESI occurring during on treatment period will be summarized. Summaries of these AESIs will be provided by subgroup (see [Section 2.2.1](#)). A listing of all grouping levels down to the MedDRA preferred terms used to define each AESI will be generated.

### **2.8.2 Deaths**

The number and percentage of deaths occurring during the on-treatment period and at any time during the study will be provided. Deaths occurring during the on-treatment period will be further summarized by system organ class and preferred term. All deaths will be listed and flagged appropriately.

### **2.8.3 Laboratory data**

On analyzing laboratory data, data from all sources (central and local laboratories) will be combined. The summaries will include all assessments available for the lab parameter collected no later than 30 days after the last study treatment administration date (see [Section 2.1.1](#)).

Grading of laboratory values will be assigned programmatically as per NCI Common Terminology Criteria for Adverse Events (CTCAE), version 4.03. The calculation of CTCAE grades will be based on the observed laboratory values only, clinical assessments will not be taken into account.

CTCAE Grade 0 will be assigned for all non-missing values not graded as 1 or higher. Grade 5 will not be used.

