#### **Study treatment**

Study treatment includes any of the following: r-ATG, CsA, eltrombopag or combination of these drugs administered to the patient as part of the required study procedures up to the end of Year 2.

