### **Date of last administration of study treatment**

The date of last administration of study treatment is derived as the last date when a nonzero dose of any component of study treatment was administered as per the DAR eCRF. (Example: if the last eltrombopag dose is administered on 15-Apr-2014, and the last dose of a combination partner is administered on 17-Apr-2014, then the date of last administration of study treatment is 17-Apr-2014).

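### SAP 2.8.3 closes the laboratory window 30 days after the last dose of any study drug, which contradicts the eltrombopag-based on-treatment period that limits all safety summaries

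*SAP*

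**What the plan says.** The laboratory section (2.8.3, identical in both SAPs) includes assessments "collected no later than 30 days after the last study treatment administration date" and refers the reader to Section 2.1.1.

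Section 2.1.1 defines the terms used there:

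- **Study treatment:** "Study treatment includes any of the following: r-ATG, CsA, eltrombopag or combination of these drugs", given "as part of the required study procedures up to the end of Year 2".
- **Date of last administration of study treatment:** "the last date when a nonzero dose of any component of study treatment was administered as per the DAR eCRF".

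The same section defines the on-treatment period differently, as running "from date of first administration of study treatment to 30 days after date of last administration of eltrombopag". It restricts safety tables and figures to that period, apart from baseline data. Section 2.8, the parent of 2.8.3, repeats the restriction and ends the period "to 30 days after the date of the last actual administration of eltrombopag". Protocol 12.5.2 has the same definition and the same restriction.

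**The concern.** The cross-reference from 2.8.3 to 2.1.1 does not settle which cut-off applies. Section 2.1.1 contains both the any-component date that 2.8.3 names and the eltrombopag-based period that governs every other safety summary. Because the sentence in 2.8.3 is the more specific rule, a programmer could reasonably apply it as written.

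The adverse event tables would then close 30 days after eltrombopag, while some laboratory tables stayed open through the CsA-only period. The two could not be read together as covering the same exposure. One laboratory value could also be flagged as post-treatment in the listing and still be counted in a summary table, although the protocol limits those tables to on-treatment data.

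This looks like an incomplete update. The July 2022 SAP history lists the on-treatment change against Section 2.1.1 only, and the sole change it lists for 2.8.3 is the ALT and AST sub-items. That is evidence of intent only; the contradiction itself lies in the current text.

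**Working it through.** The plan states no figure to reproduce, so the check is date arithmetic on its own definitions.

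**Inputs**

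- Visit days (protocol Table 8-1): Week 13 = Day 92, Week 26 = Day 183, Week 52 = Day 365, Year 2 = Day 729, Year 3 = Day 1093.
- Planned eltrombopag for responders: to Week 52 (protocol 6.1.5).
- Planned CsA for responders: at least to Year 2, with trial supply ending there (protocol 6.1.5).
- Non-responders at Week 26: study treatment stops (protocol 3 and 9.1.1).

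**Formulas.** Let E be the day of the last eltrombopag dose and C the day of the last study CsA dose, with C ≥ E.

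- End of on-treatment period = E + 30
- Cut-off as written in 2.8.3 = C + 30
- Gap = C − E

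| Case | E | C | On-treatment end | 2.8.3 cut-off | Gap (days) |
|---|---|---|---|---|---|
| Responder, planned durations | 365 | 729 | 395 | 759 | 364 |
| Eltrombopag stopped at Week 26, CsA to Year 2 (assumed) | 183 | 729 | 213 | 759 | 546 |
| Eltrombopag stopped at Week 13, CsA to Year 2 (assumed) | 92 | 729 | 122 | 759 | 637 |
| Non-responder, all drugs stopped at Week 26 | 183 | 183 | 213 | 213 | 0 |

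**What data fall in the gap.** For the responder on planned durations, Table 8-1 schedules one hematology draw between Day 395 and Day 759, at Year 2. It is inside the 2.8.3 cut-off if C + 30 ≥ 729, that is, if CsA lasts to Day 699 or later. Year 3 (Day 1093) lies outside both windows. No routine clinical chemistry is scheduled after the safety follow-up visit, so extra liver data could only be unscheduled. In the two assumed early-stop cases, the efficacy visits that continue under protocol 9.1.1 (Week 52, and after a Week 13 stop also Week 26) would fall in the gap too.

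**Which outputs depend on the 2.8.3 cut-off**

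| Output | Time limit in its own wording | Exposed? |
|---|---|---|
| Shift tables (CTC grade; low/normal/high) | worst on-treatment value | No |
| Boxplots and their tables | baseline and on-treatment time points | No |
| Worst CTC grade | post-baseline only | Yes |
| Liver categories | worst post-baseline only | Yes |
| By-visit platelets, hemoglobin, neutrophils | scheduled visits only | Yes |

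**Which analysis.** The first SAP version, dated 15-Sep-2020, preceded the first patient's first visit, so the earliest possible Day 729 is 15-Sep-2020 + 728 days = 13-Sep-2022. The last patient's first visit was on 03-Dec-2021. Allowing 30 days of screening, the last Week 26 visit falls at about 02-Jan-2022 + 182 days = 03-Jul-2022. No primary cut-off date is given. If it was set near that visit, no Year 2 hematology exists in the primary analysis, and the scheduled draw matters only in the final one.

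**The case against.** The strongest reply is that the general rule already decides the matter. Sections 2.1.1 and 2.8 confine safety tables and figures to the on-treatment period, and 2.8.3 sits under 2.8. A reader might infer from 2.8.3 alone that the sponsor chose a longer laboratory window. The documents do not support that: they contradict themselves, and most of the text favours the shorter window. This corrects how the point is framed but leaves two incompatible cut-offs in each SAP.

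A reader might also infer that the hematology shift tables would take in Year 2 counts. They would not, because both are defined by the worst on-treatment value.

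A third tempting inference is that a relapse a year after eltrombopag would be reported as an on-treatment toxicity. The exposed worst-grade table is labelled post-baseline, not on-treatment. The relapse thresholds for neutrophils and platelets are also the ones used at entry, where at least two of the three lineages must be below their cut-offs. The worst-grade table ignores baseline status, and hematology is weekly in Weeks 1 to 8. Many participants will therefore probably have their worst grade early, and a late relapse would seldom change it; this is an inference, not a demonstrated absence of effect. Relapse also requires study treatment to stop, which closes even the longer window 30 days after the last CsA dose.

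Finally, 364 days measures the window, not the amount of data. The study is single-arm and descriptive, and the adverse event, death and primary-endpoint analyses are unaffected. All of this stands, and it limits the weight of the point.

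**Conclusion.** The contradiction is real and is present in both SAPs. Read with the SAP's definitions, 2.8.3 admits laboratory values up to 30 days after the last dose of any component, whereas SAP 2.1.1, SAP 2.8 and protocol 12.5.2 stop 30 days after eltrombopag.

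The cut-offs differ by 364 days for a responder on planned durations, by more if eltrombopag stops early while CsA continues to Year 2, and by nothing for a non-responder who stops everything at Week 26. The practical effect is small. It is confined to the three exposed outputs and, on planned durations, to one scheduled hematology draw per responder still on CsA, plus unscheduled tests, mainly in the final analysis.

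This rests on the Table 8-1 visit days, on CsA continuing to about Year 2, and on a primary cut-off close to the last Week 26 visit. The text should be corrected because it would put post-treatment values into tables meant for on-treatment data, but it does not threaten the trial's conclusions.

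**What to change.** In Section 2.8.3 of both SAPs, replace the reference to the last study treatment dose with a reference to the last eltrombopag dose, so that laboratory and adverse event tables cover the same period. Later laboratory values remain in the listings, flagged as post-treatment as 2.1.1 already requires, so no data are lost. If a summary of the CsA-only period is wanted, specify it as a separate table and label it as such.

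The cost is one phrase in each SAP and a check that the programs for the three exposed outputs apply the same end date. No data collection or clinical rule changes.
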